#### 3.1 Eligibility Criteria

Participants must meet the following criteria on screening examination to be eligible to participate in the study:

- 3.1.1 Be a male  $\geq 18$  years of age.
- 3.1.2 Participants must have histologically or cytologically confirmed adenocarcinoma of the prostate without  $\geq 50\%$  neuroendocrine differentiation or small cell histology.
- 3.1.3 Participants must have progressive disease as defined by either:
  - Castrate resistant disease as defined by PCWG. Participants must have a rise in PSA on two successive determinations at least one week apart and PSA levels  $\geq 2$  ng/ml (only the screening PSA needs to be  $\geq 2$  ng/ml) and testosterone levels  $< 50$  ng/dL, OR
  - Soft tissue progression defined by RECIST 1.1, OR
  - Bone disease progression defined by PCWG2 with two or more new lesions on bone scan.
- 3.1.4 Participants must have a testosterone levels  $< 50$  ng/dL.
- 3.1.5 CRPC with metastatic disease with at least one site of metastatic disease must be amenable to needle biopsy. Soft tissue biopsy sites include: lymph node or visceral metastases. Bone sites include lumbar vertebrae, pelvic bones and long bones. Excluded sites are thoracic, cervical vertebrae, skull and rib lesions. Biopsy site will be selected with guidance of interventional radiologist determining best site to optimize balance of obtaining useful tissue for analysis and minimizing risk.
- 3.1.6 Participants without orchiectomy must be maintained on LHRH agonist/antagonist therapy.

CONFIDENTIAL

This document is confidential. Do not disclose or use except as authorized.

- 3.1.7 Participants may have had any number of previous hormonal therapies (antiandrogens, estrogens, finasteride, dutasteride, ketoconazole, abiraterone) provided these were discontinued  $\geq 4$  weeks before enrollment. Participants on prednisone 10 mg daily or another equivalent steroid dose are eligible. Participants on inhaled steroids are eligible.
- 3.1.8 Participants may have had up to two previous cytotoxic therapeutic regimens provided these were discontinued  $\geq 4$  weeks before enrollment. The use of antineoplastic agents for non-cancer therapy (i.e. colitis, rheumatoid arthritis) may be allowed provided the patient has been on a stable dose without toxicities greater than grade 1.

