## 14. STATISTICAL CONSIDERATIONS

### 14.1 Primary Analysis

The primary objective of this trial is to analyze possible AR related mechanisms of resistance to enzalutamide in serial CRPC biopsies including AR sequencing (mutations, splice variants), AR regulated gene expression, tumor androgen levels, profiling of enzymes involved in androgen synthesis/metabolism, and whole-exome and transcriptome sequencing. These data are of various forms resulting in different measures for a given participant: (a) continuous data will be evaluated by calculating mean percent change in level, (b) ordinal data will be evaluated by the mean percent change in count, and (c) categorical binary data will be evaluated by No/Yes change in status.

For the primary analysis, only participants who received at least 2 cycles of enzalutamide and experienced progression will be eligible. We plan to enroll a total of 66 participants to obtain 40 evaluable participants. A 60% overall yield is based on the assumptions that 95% of participants are eligible, 90% of these participants have paired biopsies and 70% of participants have evaluable tumors for each sample.

The target sample size is based on power to evaluate a mean percent change in level. The hypothesis is that AR reactivation can lead to resistance to enzalutamide. We will evaluate the mean percent change in a set of resistance parameters using the paired t-test. All continuous variables will be evaluated as a set. A mean percent change of 30% would be considered biologically significant. The effect size is defined as the mean percent change divided by the standard deviation (SD) of percent change, which is unknown in this population. The table below provides the mean percent change that can be detected with 80% or 90% power under various scenarios of SD given a one-sided 0.025 alpha and 40 evaluable participants. For example, there is 80% power to detect mean percent change of 22.7% given a SD of 50% corresponding to an effect size=0.454 SD. The mean percent change presented ranges from 13.6%-31.5%. Therefore, this study is designed with satisfactory power to show a biologically significant mean percent change in a set of resistance parameters.

Paired Tumor Samples (n=40)				
	Paired t-test, 1-sided alpha=0.025			
Power=80%, Effect Size=0.454 SD				
Standard Deviation	30%	40%	50%	60%
Mean Percent Change	13.6%	18.2%	22.7%	27.3%
Power=90%, Effect Size=0.526 SD				
Standard Deviation	30%	40%	50%	60%

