The two-group t-test will be used to examine the difference in level and/or change pre- to post-treatment in levels by PSA and RECIST (measurable disease participants) response outcome. Assuming 40 evaluable participants, if PSA response rate is 25% (10 responders and 30 non-responders), there is 80% power to detect an effect of 1.05 SD at a two-sided significance level of 0.05. Continuous levels may be dichotomized at the median for further evaluation. Association between response and categorical variables will be evaluated using Fisher’s exact test. Analyses of these correlative endpoints will be exploratory and adjustments will not be made for multiple comparisons.

CONFIDENTIAL

This document is confidential. Do not disclose or use except as authorized.

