## Appendix B: Required Forms at Registration

The DFCI coordinator will Fax to DFCI ODQ:

- Current IRB approved consent form signed by participant and Investigator (MD only)
- HIPAA authorization form (if separate from the informed consent document)
- Signed and dated DFCI eligibility checklist (signed by MD or RN)
- The following source documentation is typically required:
- Please note: Additional documentation may be required by the lead institution.
  - Labs for PSA values used to determine eligibility (Lab values used to determine eligibility, including screening PSA)
  - Documentation of prior treatments/procedures performed to treat prostate cancer (e.g. Chemotherapy, Cryotherapy, Hormone Therapy,
  - Radiation therapy with start and stop dates and dosing information if applicable)
  - Reports documenting disease status
    - Chest CT
    - CT or MRI Abdomen and Pelvis
    - Bone Scan
  - Pathology Report
  - Concomitant medication list
  - Progress note or equivalent documentation of consenting visit
  - Progress note documenting medical history and oncologic history
  - Screening Labs
    - Complete Blood Count with differential
    - Electrolytes
    - Liver Function Tests
    - Total Testosterone
    - PSA
    - Coagulation Factors
  - Screening visit note, with BP, vital signs, ECOG Performance status
  - Screening ECG

CONFIDENTIAL

This document is confidential. Do not disclose or use except as authorized.

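### Section 14.2 compares markers by response without regard to prior treatment, so a marker that only tracks prior treatment can appear associated with enzalutamide response if prior treatment is linked to both

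*Combined protocol and SAP*

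**What the plan says.** Section 1.3 makes it a secondary objective to correlate AR alterations, gene expression, androgens and sequencing results with PSA and radiographic response. Section 14.2 gives the method. For continuous markers: "The two-group t-test will be used to examine the difference in level and/or change pre- to post-treatment in levels by PSA and RECIST" response outcome. For categorical markers: "Association between response and categorical variables will be evaluated using Fisher’s exact test". The section calls these analyses exploratory and makes no multiplicity adjustment.

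Eligibility is broad on prior treatment. Section 3.1.7: "Participants may have had any number of previous hormonal therapies (antiandrogens, estrogens, finasteride, dutasteride, ketoconazole, abiraterone", subject to a washout. Section 3.1.8: "Participants may have had up to two previous cytotoxic therapeutic regimens", again with a washout. Neither kind of treatment is required, so treated and untreated men can both enrol.

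Sections 8.1, 14.1 and 14.2 do not stratify, adjust or subgroup by prior treatment. The information is requested, however: Appendix B lists "Documentation of prior treatments/procedures performed to treat prostate cancer" among the source documents for registration, and section 3.7.1 of Appendix E repeats it.

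**The concern.** A two-group comparison of marker levels by response attributes any difference to response. Suppose that men already treated with abiraterone or ketoconazole differ in a marker, and also respond less often to enzalutamide. Non-responders would then contain more pre-treated men, and the marker would differ between the groups even if it told us nothing about response among men with the same treatment history. The same argument applies to prior chemotherapy.

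The label of exploratory does not deal with this. Section 14.2 attaches it to multiple comparisons, that is, to chance findings. Confounding is systematic: it can push several related markers the same way, and a larger sample does not remove it. At stake is how a reported marker-response association is read, under a named secondary objective.

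**Working it through.** **Inputs from the documents.** "We plan to enroll a total of 66 participants to obtain 40 evaluable participants" (section 14.1). Section 14.2 takes 25% PSA response, hence 10 responders and 30 non-responders, and states that "there is 80% power to detect an effect of 1.05 SD at a two-sided significance level of 0.05".

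**The plan's own figure.** With 10 v 30, the standard error in SD units is √(1/10 + 1/30) = 0.365. The noncentrality at 1.05 SD is 1.05/0.365 = 2.88 on 38 df. The noncentral t distribution gives power of 80.0%, and a detectable effect at 80% power of 1.0498 SD. The stated figure reproduces.

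**Assumptions, because the documents do not give them.** Half of the 40 men are pre-treated. The marker is normal with SD 1, shifted by a set amount in pre-treated men. Within each prior-treatment group, marker and response are unrelated.

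**How the spurious difference arises.** Expected difference = shift × (pre-treated share of responders − pre-treated share of non-responders).
- Response 40% untreated v 10% pre-treated: 8 + 2 responders and 12 + 18 non-responders. The difference is shift × (2/10 − 18/30) = −0.40 × shift.
- Response 35% v 15%: 7 + 3 responders and 13 + 17 non-responders. The difference is shift × (3/10 − 17/30) = −0.27 × shift.
- Response 25% v 25%: 5 + 5 and 15 + 15. The difference is zero.

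**Hand check, 40% v 10%, shift 1 SD.** Mixing raises the within-group variances to 1 + 0.2 × 0.8 = 1.16 and 1 + 0.6 × 0.4 = 1.24. Pooled: (9 × 1.16 + 29 × 1.24)/38 = 1.22, so SD = 1.105. Then 0.40/(1.105 × 0.365) = 0.99, and the two-sided 5% test rejects with probability of about 17% by normal approximation.

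**Simulation** (6,000 trials per scenario, two-sided 0.05), false-positive rate of the unadjusted t-test:

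| Marker shift | 25% v 25% | 35% v 15% | 40% v 10% |
|---|---|---|---|
| 0.5 SD | about 5% | 6.2% | 8.2% |
| 0.8 SD | about 5% | 7.9% | 12.9% |
| 1.0 SD | about 5% | 9.8% | 15.7% |
| 1.2 SD | about 5% | 11.6% | 18.9% |

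Repeat runs, one with 60,000 trials per scenario, agree to about one percentage point. I therefore quote 6% to 9% at 0.5 SD and 8% to 20% at 0.8 to 1.2 SD. A linear model with prior treatment as a covariate rejects in about 5% of trials in every cell.

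**Fisher's exact test.** With marker prevalence of 20% v 50% or 15% v 60% by prior treatment (assumed), it rejected in 4% to 10% of trials, against about 3% without confounding. The effect is smaller because the test is conservative.

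**Cost of adjusting.** The variance factor of the adjusted response effect is 1/Σ(responders × non-responders/stratum size).
- Balanced, 5/10 v 15/30: 1/(3.75 + 3.75) = 0.133, detectable effect 1.05 SD.
- 3/10 v 17/30: 1/(2.55 + 4.55) = 0.141, detectable effect 1.08 SD.
- 2/10 v 18/30: 1/(1.8 + 4.8) = 0.152, detectable effect 1.12 SD.

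**The case against.** The strongest objection is that both links come from outside the documents. Section 2.4 lists AR mutation, splice variants and steroidogenic enzymes as mechanisms of resistance to castration. Every participant is castrate (3.1.4, 3.1.6), so that list does not separate abiraterone- or ketoconazole-treated men from the rest. On chemotherapy, section 2.1 reports PSA declines of more than 50% in 56% of the phase I/II study, whose expansion cohorts were half pre- and half post-chemotherapy, and a 54% rate in the post-docetaxel phase 3 trial. Doses differed, so the comparison is rough, but it does not suggest a large gap. This stands: a reader might infer that the correlative findings will be confounded, and the documents support only that they can be.

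Second, adjustment is not always right. The trial's hypothesis is that AR reactivation causes resistance. If prior treatment selects an AR alteration and that alteration causes non-response, the marker mediates the effect and adjustment removes real signal. A simulation of this case (40 men, 20 pre-treated, shift 0.8 to 1.2 SD, logistic slope 0.8 to 1.2 per SD, overall response about 25% to 28%, all assumed) lost about 6 to 15 points of power: 57% to 91% unadjusted, 48% to 79% adjusted. This also stands. It is the reason to add an adjusted analysis and not to replace the planned tests.

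Third, the objective is to correlate, the analyses are exploratory, and per-test error is not controlled across many markers. That limits the weight of the point but does not tell a reader whether an association merely reflects treatment history.

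A reader might also infer that a single-arm trial cannot separate a marker of prior treatment from a marker of response because it has no comparator. That does not follow. A control arm separates prognostic from predictive markers; confounding by a measured baseline factor can be handled within one arm.

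**Conclusion.** The point holds in a conditional form. Eligibility mixes prior treatments, the tests in 14.2 ignore them, and the information is requested at registration. If prior treatment is linked to both marker and response, the unadjusted comparison can mislead. Under the assumptions above, the false-positive rate runs from about 5% (response unrelated to prior treatment) through 6% to 9% (0.5 SD shift) to 8% to 20% (0.8 to 1.2 SD, response 35% v 15% or 40% v 10%). The documents do not say where in that range the trial lies.

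The concern bears mainly on baseline level. Change from pre- to post-treatment is affected only if change also differs by prior treatment. A reader might extend the point to the primary analysis or to the 1.05 SD power statement. Neither is touched: the primary test is paired within participant and does not compare responders with non-responders, and the power figure reproduces.

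**What to change.** In section 14.2, keep the two-group t-test and Fisher's exact test, and pre-specify beside them:
- a linear model of marker level (or change) on response plus prior abiraterone/ketoconazole (yes/no);
- the same model with prior chemotherapy (yes/no) added, as a sensitivity analysis;
- for categorical markers, the response tables shown separately by prior abiraterone/ketoconazole. With about 10 responders, a stratified exact test would be too sparse to replace Fisher's test.

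Report both sets of results. Describe a marker as associated with response independently of prior treatment only if the adjusted estimate supports it.

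The cost is one degree of freedom for the main covariate, a detectable effect of about 1.05 to 1.12 SD instead of 1.05 SD, and a conservative adjusted estimate if the marker mediates the effect of prior treatment. About 10 responders support one or two covariates and no more. Appendix B calls the source documents typically required, and the form list in section 12.1.2 names no prior-therapy field, so the sponsor should confirm that the yes/no items are coded; some abstraction from source may be needed.

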### 1.3 Secondary Objectives

- Assess changes in serum androgen concentrations (including testosterone, dihydrotestosterone (DHT), and androgen precursors) between baseline and subsequent assessment visits.
- To assess prostate specific antigen (PSA) response to enzalutamide.
- To assess PSA response duration to enzalutamide.
- To assess response of measurable disease to enzalutamide.
- To assess duration of response of measurable disease to enzalutamide.
- To assess safety and tolerability of enzalutamide.
- To correlate alterations in AR mutation, AR splice variants, TMPRSS2/ERG, AR regulated gene expression, tumor androgens, serum androgens, whole-exome and transcriptome sequencing with PSA and radiographic response to enzalutamide.

CONFIDENTIAL

This document is confidential. Do not disclose or use except as authorized.

- To investigate subsequent lines of therapy, including line of agent, name of agent, and PSA kinetics following study drug discontinuation and correlate with response to study drug.

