### 8.1 Statistical Data Analysis

Determination of biological and molecular endpoints to analyze possible AR related mechanisms of resistance to enzalutamide in serial tumor biopsies will occur as follows:

- AR sequencing
  - Mutations – continuous variable from microarray data
  - TMPRSS2:ERG translocation status – categorical variable from PT PCR (yes vs. no)
  - AR splice variants – categorical variable from RT PCR (native vs. alternative)
- AR regulated gene expression – continuous variable from microarray data
- Tumor androgen levels – continuous variable from mass spectroscopy data
- Profiling of enzymes involved in androgen synthesis/metabolism – continuous variable from microarray data

CONFIDENTIAL

This document is confidential. Do not disclose or use except as authorized.

- Whole-exome and transcriptome sequencing – continuous variable from sequencing analysis

Continuous data will be evaluated by calculating mean percent change in level. Categorical data will be evaluated by yes/no change in status. Ordinal/count number data will be evaluated by mean percent change in total count.

CONFIDENTIAL

This document is confidential. Do not disclose or use except as authorized.

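### Section 14.2 waives all multiplicity adjustment for the response correlations, which include exome and transcriptome data, so a feature-level screen would carry no stated error rate

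*Combined protocol and SAP*

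**What the plan says.** Among the secondary objectives, section 1.3 lists the correlation of several AR-axis measures and of "whole-exome and transcriptome sequencing with PSA and radiographic response to enzalutamide". Section 1.4 lists the exploratory objectives separately, and this correlation is not among them.

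Section 8.1 describes the form of the sequencing data in one line: "Whole-exome and transcriptome sequencing – continuous variable from sequencing analysis". It gives no number of features and no summary score.

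Section 14.2 sets the tests. For continuous measures: "The two-group t-test will be used to examine the difference in level and/or change pre- to post-treatment in levels by PSA and RECIST" response, the RECIST comparison being confined to participants with measurable disease. For categorical measures: "Association between response and categorical variables will be evaluated using Fisher’s exact test". It also allows a further split: "Continuous levels may be dichotomized at the median for further evaluation". Power is given for a single comparison with 10 PSA responders and 30 non-responders at two-sided 0.05: "there is 80% power to detect an effect of 1.05 SD".

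The section closes with the rule at issue: "Analyses of these correlative endpoints will be exploratory and adjustments will not be made for multiple comparisons". It makes no exception for any data type. The plan gives no feature filter, false-discovery limit or validation step.

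**The concern.** Waiving adjustment is reasonable for a short, named list of AR measures that readers can count for themselves. The same sentence, read with section 1.3, also covers data that can yield thousands of features. A screen of that size at a nominal 0.05 produces a long list whatever the truth, and the power statement, written for one comparison, says nothing about how trustworthy that list is.

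At stake is the interpretation of a secondary objective whose results are meant for a peer-reviewed report (section 15). Without the number of features tested or a false-discovery estimate, a reader cannot separate a list that is largely signal from one that is largely chance.

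**Working it through.** **Inputs from the plan.** 10 responders and 30 non-responders, two-sided alpha 0.05, effect 1.05 SD, stated power 80% (section 14.2). The plan does not give the number of features tested, m, or the share p of features truly associated with response. Both are assumptions here and are shown as ranges.

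**1. The plan's own figure.** Two-group t-test, df = 10 + 30 − 2 = 38, noncentrality = 1.05 / √(1/10 + 1/30) = 1.05 / 0.365 = 2.88. The noncentral t distribution gives power of 80.0%, so the stated figure reproduces for one test. With the same split, power is 52% at 0.75 SD and 27% at 0.5 SD.

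**2. Chance hits when no feature is associated.** Expected number = 0.05 × m for each response outcome, with one test per feature. This expectation does not need the tests to be independent. The family-wise error rate, 1 − 0.95^m, does.

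| m (assumed) | Expected chance hits | Family-wise error rate |
|---|---|---|
| 10 | 0.5 | 40% |
| 100 | 5 | 99.4% |
| 1,000 | 50 | about 100% |
| 20,000 | 1,000 | about 100% |

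Section 14.2 permits level and change, two response outcomes, and a t-test or a median split. A continuous feature could therefore be tested in up to 2 × 2 × 2 = 8 correlated ways. The table counts only one.

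**3. False share of the hits.** This depends on p and on power, not on m alone:

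false share = 0.05(1 − p) / [0.05(1 − p) + power × p]

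At 80% power:

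| p (assumed) | False share |
|---|---|
| 50% | 5.9% |
| 20% | 20% |
| 10% | 36% |
| 5% | 54% |
| 1% | 86% |
| 0.1% | 98% |

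Setting the false share to one half gives p = 0.05 / (0.05 + power):
- 80% power: 0.05/0.85 = 5.9%
- 50% power: 0.05/0.55 = 9.1%
- 30% power: 0.05/0.35 = 14.3%

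Most hits are false only when p is below these values.

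**4. Worked example.** Assume m = 20,000 with 1% (200) truly associated at 1.05 SD. False hits: 0.05 × 19,800 = 990. True hits: 0.80 × 200 = 160. False share: 990/1,150 = 86%.

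**5. Why Bonferroni is not the answer.** At m = 20,000 the per-test alpha is 0.05/20,000 = 0.0000025. Power at 1.05 SD falls to 1.3%, and the effect detectable with 80% power rises to 2.37 SD.

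**The case against.** The strongest reply is that the plan never says sequencing will be tested gene by gene. Section 8.1 treats it as one line, section 14.1 says that continuous variables in the primary analysis are evaluated as a set, and the text leading into the tests in 14.2 speaks of a set of AR resistance measures without naming the exome or transcriptome. If sequencing enters as a few pathway scores, the counts of 50 to 1,000 disappear. This stands as a limit on the size of the problem, which is why every count above is conditional. It does not remove the point. Section 14.1 itself lists sequencing among the resistance measures, section 1.3 requires its correlation with response, and nothing in 14.2 restricts the number of features.

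A second reply is that the analyses are openly labelled exploratory. That also stands: no confirmatory type I error claim is broken. But the label discloses the absence of control without giving readers an error rate.

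Third, the figures do not carry over to every test. The 1.05 SD figure is for PSA response under one assumed split, and RECIST comparisons may have fewer than 40 participants. Fisher's exact test can fall well below its nominal rate for rare alterations. With 10 versus 30, an alteration present in 2 of 40 participants has a smallest possible p of 45/780 = 0.058, so it cannot be a chance hit at 0.05. The counts are therefore best read as applying to continuous, transcript-type features.

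**Conclusion.** The point holds in conditional form. The waiver in 14.2 has no exception and, through section 1.3, reaches exome and transcriptome data. If those data are screened feature by feature at 0.05, the resulting list has no stated error rate. The expected number of chance hits is about 50 to 1,000 per response outcome for an assumed 1,000 to 20,000 features with all nulls true.

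A reader might infer three stronger things that the documents do not support:
- That the hits would be mostly false as a matter of course. This needs a truly associated share below about 6% at 80% power, 9% at 50% or 14% at 30%. That is plausible for an unselected transcriptome screen, but the plan gives no such figure, and it need not apply to the short AR list.
- That unadjusted p-values carry no evidential meaning. What is missing is an error rate for the list.
- That the 1.05 SD figure shows true signals to be few. It is the effect with 80% power, not the smallest detectable effect, and power says nothing about how many associations exist.

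This is a weakness of reporting and interpretation. It should be corrected, but it does not threaten the primary analysis.

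**What to change.** In section 14.2:
- State the level at which sequencing data enter the response correlations (individual features or named summary scores) and report the number of features tested.
- Limit the no-adjustment sentence to the named AR-axis measures, with nominal p-values labelled exploratory.
- For any exome- or transcriptome-wide feature-level tests against PSA or RECIST response, report Benjamini-Hochberg q-values, for example with a 10% threshold.
- Reconcile the secondary status in section 1.3 with the exploratory label in 14.2.

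The cost is a few lines of plan text and one routine analysis step, with no added participants, samples or assays. The real downside is that fewer genes will be called significant, and with about 40 evaluable participants possibly very few. Unadjusted p-values can still be shown beside the q-values, so no information is lost.
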